### **3.8.2 Prohibited Concomitant Medications**

The use of systemic steroid therapy and other immunosuppressive drugs is not allowed except for the treatment of infusion reaction, irAEs, and for prophylaxis against imaging contrast dye allergy or replacement-dose steroids in the setting of adrenal insufficiency (providing this is <10 mg/day prednisone or equivalent), or transient exacerbations of other underlying diseases such as COPD requiring treatment for  $\leq$  3 weeks. If systemic corticosteroids are required for the control of infusion reactions, pyrexia or irAEs, it must be tapered and be at non-immunosuppressive doses (< 10 mg/day of prednisone or equivalent) before the next administration of study treatment.

If the dose of prednisone or equivalent cannot be reduced to less than 10 mg/day before the administration of next dose of study treatment then spartalizumab must be discontinued.

The use of live vaccines is not allowed through the whole duration of the study. Inactivated vaccines are allowed.

Dabrafenib induces CYP3A4- and CYP2C9- mediated metabolism and may induce other enzymes including CYP2B6, CYP2C8, CYP2C19 and UDP glucuronosyltransferases (UGT). Dabrafenib may also induce transporters (e.g., P-glycoprotein (P-gp)). Co-administration of dabrafenib and medicinal products which are affected by the induction of CYP3A4 or CYP2C9 such as hormonal contraceptives, warfarin or dexamethasone may result in decreased concentrations and loss of efficacy. If co-administration of these medications is necessary, monitor subjects for loss of efficacy or consider substitutions of these medicinal products. Use caution if co-administration of CYP2C or CYP3A4 substrates with narrow therapeutic index is required. Refer to the dabrafenib label for further information.

Based on *in vitro* and *in vivo* data, trametinib is unlikely to significantly affect the pharmacokinetics of other medicinal products via interactions with CYP enzymes or transporters.

## **4.0 STUDY ASSESSMENTS**

#### 4.1 CRITICAL BASELINE ASSESSMENTS

Baseline (Screening) assessments obtained will include:

- Documentation of relevant medical history Complete physical examination, including weight and single height measurement
- Review of concomitant medications and documentation baseline toxicity information
- Verification of BRAF mutation at V600 position by a CLIA certified assay. Presence of BRAF by IHC is acceptable to begin screening evaluations.
- Documentation of surgical resectability from multi-disciplinary tumor conference
- Vital signs: blood pressure, temperature, respiratory rate, pulse rate
- Eastern Cooperative Oncology Group (ECOG) performance status
- Clinical laboratory tests: hematology, thyroid (TSH and fT4) and clinical chemistry
- Coagulation Panel (PT/PTT)
- Serum or urine beta-human chorionic gonadotropin ( $\beta$ -HCG) pregnancy test for female subjects of childbearing potential only
- 12-lead electrocardiogram (ECG)
- 2D complete echocardiogram for assessment of ejection fraction
- Ophthalmic exam by ophthalmologist to include indirect fundoscopic examination, visual acuity, visual field examination, tonometry, and direct fundoscopy, with special attention to retinal abnormalities that are predisposing factors for RVO or CSR
- Brain magnetic resonance imaging (MRI) with contrast or a computed tomography (CT) scan (with/without contrast) if MRI is contraindicated
- CT of the chest, abdomen and pelvis with contrast or PET/CT, imaging of body site of interest (neck, extremity) if indicated
- Research blood collection
- Research microbiome collection
- Research tumor biopsy

#### 4.2 BASELINE CONFIRMATION OF BRAF MUTATION-POSITIVE MELANOMA

Patients may be enrolled and started on study if they have local molecular testing that is positive for BRAF mutation in the V600 position by a CLIA certified assay. Only patients with V600E or V600K mutations are eligible for enrollment. Presence of BRAF by IHC is acceptable to begin screening evaluations.

## 4.3 SCHEDULE OF ASSESSMENTS

**Table 10 Time and Event Table—Neoadjuvant Phase**

	Screening J	Cycle 1	Cycle 1	Cycle 2	Cycle 2
		Day 1	Day 15 K	Day 1 K	Day 28 K
Informed consent	X				
Demographics	X				
Medical history	X				
Concurrent medications	X	X	X	X	X
AEs a	X	X	X	X	X
PE/Vitals/ECOG	X	X	X	X	X
Pregnancy test b	X				
CBC with diff c	X	X	X	X	X
Serum chemistry	X	X	X	X	X
Thyroid TSH, fT4	X				X
Coagulation	X				X
Echocardiogram	X				
12-lead EKG	X		X		X
Ophthalmic exam	X				
Research Tissue d	X				X (surgery)
Research Blood e	X		X	X	X

Research microbiome Collection f	X				X
Disease Assessment g	X				X
Surgical resection h					X
Dabrafenib and trametinib i		Continuous Daily Dosing			

- a. Systolic and diastolic blood pressure, pulse rate, temperature, including weight and single height measurement.
- b. Serum or urine  $\beta$ -hCG - For women of childbearing potential only within 7 days of start of study drugs.
- c. Albumin, alkaline phosphatase, total bilirubin, bicarbonate, BUN, calcium, chloride, creatinine, glucose, LDH, magnesium, phosphorus, potassium, total protein, AST, ALT, sodium
- d. Mandatory biopsy at baseline and collection of residual tumor at surgery.
- e. 50ml of blood will be obtained at each time point for correlative correlates
- f. OMNIgene gut kits, or equivalent, will be provided for stool collection at screening and Cycle 2
- g. PET/CT or CT of the chest, abdomen, pelvis (neck if clinically indicated) and brain MRI (or CT of the head with contrast if MRI is contraindicated).
- h. Surgical resection of residual tumor if restaging scans show disease stability or response. If disease progression is confirmed, surgery may still occur if disease is still deemed resectable
- i. Dabrafenib and trametinib will be held starting the day prior to planned surgical intervention.
- j. Screening is defined as within 35 days prior to treatment initiation.
- k. +/- 7 days

**Table 11 Adjuvant Time and Event Table for Pathologic Complete Responders  
(dabrafenib and trametinib only)**

	Post-operative	Week 12 i	Week 16 i	Week 20 i	Week 24 i	Week 28 i	Week 32 i	Week 36 i	Week 40 i	Week 44 i	Week 48 i	Week 52 i	EOT j	
Concurrent medications	X	X	X	X	X	X	X	X	X	X	X	X	X	
AEs	X	X	X	X	X	X	X	X	X	X	X	X	X	
PE/Vitals/ECO G a		X	X	X	X	X	X	X	X	X	X	X	X	
CBC with diff		X	X	X	X	X	X	X	X	X	X	X	X	
Serum chemistry b		X	X	X	X	X	X	X	X	X	X	X	X	
TSH, fT4				X		X			X					
Echocardiogram c		X			X			X			X			
12-lead EKG		X			X			X			X		X	
Research Biopsy d			If evidence of disease recurrence or metastasis											

Research Blood e		X			X			X			X		X
Research microbiome collection f		X						X					X
Disease Assessment g				X			X			X			X
Dabrafenib and trametinib dosing	X	Continuous Daily Dosing											

- a. Includes systolic and diastolic blood pressure, pulse rate, temperature and weight.
- b. Albumin, alkaline phosphatase, total bilirubin, bicarbonate, BUN, calcium, chloride, creatinine, glucose, LDH, magnesium, phosphorus, potassium, total protein, AST, ALT, sodium.
- c. Repeat echocardiogram will be performed at month 3 and 6 and at the discretion of the investigator if there are symptoms concerning for heart failure.
- d. Should a biopsy be performed as part of standard practice, this study may request up to 4 additional cores for correlative studies.
- e. 50ml of blood will be obtained at each time point for correlative correlates.
- f. Microbiome will be collected at week 12, 36 and at recurrence. OMNIgene kits, or equivalent, will be provided
- g. PET/CT or CT of the chest, abdomen, pelvis (neck if clinically indicated) and brain MRI (or CT of the head with contrast if MRI is contraindicated).
- h. Dabrafenib and trametinib combination therapy will resume approximately two days after the patient is able to resume normal oral intake and ideally should be within 2 weeks of date of surgery. This visit could be a telephone assessment by research nurse
- i. These time points are +/- 7 days.
- j. End of treatment is defined as completion of 44 weeks of adjuvant dabrafenib/trametinib, experiencing SAE or intolerable

AE mandating discontinuation of treatment or the development of progressive disease.

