**Figure 1: Study Overview**

### 3.1 Inclusion Criteria

A subject will be eligible for inclusion in this study only if all of the following criteria apply:

- Capable of giving written informed consent, which includes compliance with the requirements and restrictions listed in the consent form
- Patients must have histologically or cytologically confirmed clinically detected, node involved Stage IIIB/C/D melanoma by AJCC version 8 and surgically resectable disease. The definition of resectability can be determined by the patient's surgical oncologist and verified via discussion at Multidisciplinary Tumor Conference attended by melanoma medical and surgical oncology staff. Resectable tumors are defined as having no significant vascular, neural or bony involvement that would preclude complete resection or necessitate the use of adjuvant radiation. Only cases where a complete surgical resection with tumor-free margins can safely be achieved are defined as resectable.
- BRAF mutation-positive melanoma (V600E or V600K) based on report from a CLIA certified laboratory.
- Patients must have measurable disease, defined by RECIST 1.1
- Patients who have been previously treated in the adjuvant setting with ipilimumab or interferon alpha or investigational vaccines for melanoma will be eligible for treatment after a 28 day wash-out period
- Patients who have previously received anti PD-1 in the adjuvant setting will be allowed if it has been six months or longer since previous drug exposure
- Age >=18 years
- ECOG performance status 0-1 (See Appendix A)
- Women of childbearing potential, defined as all women physiologically capable of becoming pregnant will be required to use highly effective methods of contraception during dosing and for 150-days after stopping treatment with spartalizumab. Highly effective contraception methods include:
  - Highly effective contraception methods include:
    - a. Total abstinence (when this is in line with the preferred and usual lifestyle of the subject). Periodic abstinence (e.g., calendar, ovulation, symptothermal, post-ovulation methods) and withdrawal are not acceptable methods of contraception.

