    - b. Female sterilization (have had surgical bilateral oophorectomy with or without hysterectomy), total hysterectomy, or tubal ligation at least six weeks before taking study treatment. In case of oophorectomy alone, only when the reproductive status of the woman has been confirmed by follow up hormone level assessment.
    - c. Male sterilization (at least 6 months prior to screening). The vasectomized male partner should be the sole partner for that subject
    - d. Placement of a non-hormonal intrauterine device (IUD) or intrauterine system (IUS) with a documented failure rate of less than 1% per year.

Notes:

- Double-barrier contraception: condom and occlusive cap (diaphragm or cervical/vault caps) with a vaginal spermicidal agent (foam/gel/cream/suppository) are not considered highly effective methods of contraception.
- Hormonal-based methods (e.g., oral contraceptives) are not considered as highly effective methods of contraception due to potential drug-drug interactions with dabrafenib.

- Women are considered post-menopausal and not of child bearing potential if they have had 12 months of natural (spontaneous) amenorrhea with an appropriate clinical profile (i.e. age appropriate, history of vasomotor symptoms) or have had surgical bilateral oophorectomy (with or without hysterectomy), total hysterectomy, or tubal ligation at least six weeks ago. In the case of oophorectomy alone, only when the reproductive status of the woman has been confirmed by follow up hormone level assessment is she considered not of childbearing potential.
- Sexually active males must use a condom during intercourse while on treatment and for 150 days after stopping treatment with spartalizumab and should not father a child in this period. A condom is required to be used by vasectomized men as well during intercourse in order to prevent delivery of the drug via semen
- Organ function as defined below in Table 1:

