- Class II, III, or IV heart failure as defined by the New York Heart Association (NYHA) functional classification system
- Pregnant or lactating female
- Unwillingness or inability to follow the procedures required in the protocol
- Uncontrolled diabetes, hypertension or other medical conditions that may interfere with assessment of toxicity

Subjects with known glucose 6 phosphate dehydrogenase (G6PD) deficiency

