**Table 12 Adjuvant Time and Event Table for Pathologic Non-Responders (spartalizumab, dabrafenib and trametinib)**

	Post Operat iv eh	Week 12 i	Week 16 i	Week 20 i	Week 24 i	Week 28 i	Week 32 i	Week 36 i	Week 40 i	Week 44 i	Week 48 i	Week 52 i	EOT j
Concurrent medications	X	X	X	X	X	X	X	X	X	X	X	X	X
AEs	X	X	X	X	X	X	X	X	X	X	X	X	X
PE/Vitals/ECO Ga		X	X	X	X	X	X	X	X	X	X	X	X
CBC with diff		X	X	X	X	X	X	X	X	X	X	X	X
Serum chemistry b		X	X	X	X	X	X	X	X	X	X	X	X
TSH, fT4				X			X			X			
Echocardiogram c		X			X			X			X		
12-lead EKG		X			X			X			X		X
Research Biopsy d													
If evidence of disease recurrence or metastasis													
Research Blood e		X			X			X			X		X
Research microbiome collection f		X						X					X

Disease Assessment g				X			X			X			X
Spartalizumab		X	X	X	X	X	X	X	X	X	X		
Dabrafenib and trametinib dosing	X	Continuous Daily Dosing											

- a. Includes systolic and diastolic blood pressure, pulse rate, temperature and weight.
- b. Albumin, alkaline phosphatase, total bilirubin, bicarbonate, BUN, calcium, chloride, creatinine, glucose, LDH, magnesium, phosphorus, potassium, total protein, AST, ALT, sodium.
- c. Repeat echocardiogram will be performed at month 3 and 6 and at the discretion of the investigator if there are symptoms concerning for heart failure.
- d. Should a biopsy be performed as part of standard practice, this study may request up to 4 additional cores for correlative studies.
- e. 50ml of blood will be obtained at each time point for correlative correlates.
- f. Microbiome will be collected at week 12, 36 and at recurrence. OMNIgene kits, or equivalent, will be provided
- g. PET/CT or CT of the chest, abdomen, pelvis (neck if clinically indicated) and brain MRI (or CT of the head with contrast if MRI is contraindicated).
- h. Dabrafenib and trametinib combination therapy will resume approximately two days after the patient is able to resume normal oral intake and ideally should be within 2 weeks of date of surgery. This visit could be a telephone assessment by research nurse
- i. These time points are +/- 7 days.
- j. End of treatment is defined as completion of 44 weeks of adjuvant dabrafenib/trametinib, experiencing SAE or intolerable AE mandating discontinuation of treatment or the development of progressive disease

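### The protocol schedules one pregnancy test, at Screening, and none before the first spartalizumab infusion, during about 52 weeks of dosing, or at end of treatment (minor, patient safety only)

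*Combined protocol and SAP*

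**What the plan says.** Section 4.1 includes a serum or urine beta-hCG "pregnancy test for female subjects of childbearing potential only" in its list of baseline (Screening) assessments. Table 10, the neoadjuvant schedule, has a pregnancy test row with a single mark, under Screening. Footnote b sets the timing: "For women of childbearing potential only within 7 days of start of study drugs".

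Table 11 ("Adjuvant Time and Event Table for Pathologic Complete Responders") and Table 12, for patients without a pCR, have no pregnancy row and no footnote on pregnancy at the post-operative visit, at Weeks 12 to 52, or at end of treatment (EOT). The hematology and chemistry lists in Section 4.5 and the chemistry footnotes to the tables contain no hCG.

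Elsewhere, pregnancy appears in three places:

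- **Section 3.1:** women of childbearing potential "will be required to use highly effective methods of contraception during dosing and for 150-days after stopping treatment with spartalizumab". Hormonal methods do not count.
- **Section 3.2:** the entry exclusion "Pregnant or lactating female".
- **Section 5.3, Pregnancies:** a pregnancy on study treatment is to be reported to the drug supplier within 24 hours of the investigator learning of it, and followed to outcome.

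None of these schedules a repeat test. The Pregnancies text does not say that dosing stops, and the EOT definition does not list pregnancy as a reason.

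**The concern.** The protocol requires contraception throughout dosing and for 150 days after spartalizumab, so it treats conception on treatment as a risk worth guarding against. Its one laboratory check, however, comes before the first dose of anything. A third drug is added about 12 weeks later for patients without a pCR, and no test is scheduled at that point. Restaging CT or PET/CT of the chest, abdomen and pelvis, followed by surgery, falls at Cycle 2 Day 28, also without a re-check.

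If contraception fails, an early pregnancy may not show at examination or adverse event review while daily dosing continues. Exposure would be to two drugs in pCR patients, and in anyone before Week 12, and to three drugs in non-pCR patients from Week 12. The 24-hour reporting rule cannot help until somebody knows. What is at stake is the length of avoidable fetal exposure. The primary analysis, the error rate and the sample size are not touched.

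**Working it through.** This is calendar arithmetic on the schedule tables.

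**Inputs**

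- Pregnancy test: 0 to 7 days before neoadjuvant Day 1 (Table 10, footnote b, read with the Screening mark).
- Cycle length: 28 days (Section 3.6.1).
- Visit windows: +/- 7 days for Cycle 2 Day 1 and Cycle 2 Day 28 (Table 10, footnote k) and for the adjuvant weeks (Tables 11 and 12, footnote i).
- First spartalizumab infusion: Week 12; last: Week 48 (Table 12).
- Treatment: 8 weeks neoadjuvant plus 44 weeks adjuvant (Section 3.0).

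**The plan's own figure.** 8 + 44 = 52 weeks = 364 days, which agrees with the one year of therapy stated in Section 3.0. It is nominal, because dosing is interrupted around surgery.

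**Elapsed days after Day 1**

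| Visit | Nominal | With window |
|---|---|---|
| Cycle 2 Day 1 | 28 | 21 to 35 |
| Cycle 2 Day 28 | 28 + 27 = 55 | 48 to 62 |
| Week 12 | 12 x 7 = 84 | 77 to 91 |
| Week 48 | 48 x 7 = 336 | 329 to 343 |
| Week 52 | 52 x 7 = 364 | 357 to 371 |

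**Current schedule: time since the only test**

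- To the first infusion: 77 + 0 = 77 days at least, 91 + 7 = 98 days at most.
- To the tenth infusion (Weeks 12, 16, ..., 48 make ten): 329 to 343 + 7 = 350 days.
- To the Week 52 visit: 357 to 371 + 7 = 378 days.

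If Week 12 meant the first day of the twelfth week (day 77), the first range would be 70 to 77 + 7 + 7 = 91 days. The finding would be the same.

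**With a test at Cycle 2 Day 1, Cycle 2 Day 28 and every 4-weekly visit from Week 12: longest interval between tests**

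- Baseline to Cycle 2 Day 1: 35 + 7 = 42 days.
- Cycle 2 Day 1 to Cycle 2 Day 28: 62 - 21 = 41 days.
- Cycle 2 Day 28 to Week 12: 91 - 48 = 43 days.
- Between 4-weekly visits: 28 + 7 + 7 = 42 days.

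The maximum is 43 days, provided visits stay inside their windows.

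**Tests added for a patient who completes treatment.** Two in Table 10, plus eleven at Weeks 12, 16, ..., 52, gives 13. Completing 44 adjuvant weeks is itself the EOT point, so Week 52 and EOT are counted once. A patient who stops early has fewer, with the last at her EOT visit.

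**The case against.** The strongest reply is that the risk is already well controlled. Entry requires a negative status. The accepted methods are abstinence, sterilization, a vasectomized sole partner, or a non-hormonal IUD or IUS. Adverse events are reviewed at every visit, and patients are examined at each neoadjuvant visit and from Week 12 on. CT or PET/CT covering the abdomen and pelvis is scheduled at Cycle 2 Day 28, Weeks 20, 32 and 44, and EOT. Most of this stands, and it is why the point is minor. These measures prevent pregnancy or may reveal an established one. They are not early detection, and the imaging is itself an exposure that a test should precede.

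It could also be argued that footnote b's reference to starting study drugs covers the start of spartalizumab. That is hard to sustain. The footnote belongs to the neoadjuvant table, its only mark is at Screening, and Table 12 has no matching row.

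Three stronger readings are tempting, and the documents do not support them:

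- **That a pregnancy could pass unnoticed for 350 or 378 days.** Those figures are intervals in the test schedule. Examinations and repeated pelvic imaging make such a delay implausible.
- **That Section 3.8.2 creates a testing duty that the schedule then misses.** For medicines affected by dabrafenib, hormonal contraceptives among them, it says "If co-administration of these medications is necessary, monitor subjects for loss of efficacy or consider substitutions of these medicinal products". This is a general enzyme-induction warning that also names warfarin and dexamethasone. Section 3.1 already refuses hormonal methods because of that interaction.
- **That patients will not be tested at all.** Section 3.1 binds patients to requirements in the consent form, and those pages were not available. Sites may also test on their own initiative. The protocol's schedule simply does not require it.

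**Conclusion.** The gap is real and follows directly from the tables. One pregnancy test is scheduled, and none falls before the first spartalizumab infusion (77 to 98 days later), during about 52 weeks of dosing, or at EOT. It is a minor patient-safety point that is cheap to repair.

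The day counts assume that weeks are elapsed time from neoadjuvant Day 1, that visits stay within their windows, and that the baseline test is done in the week before Day 1. A late operation could lengthen the wait for the first infusion.

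No expected number of pregnancies is offered. The documents do not give the number of women of childbearing potential. The only failure rate they state, "with a documented failure rate of less than 1% per year", applies to the IUD or IUS. The COMBI-I figure of 17% in Section 3.3.1 is a share of patients who stopped the triplet for toxicity, so it cannot be used as a share of dosing time lost. A reader might want such a count to rank the issue. It would rest on assumptions alone, and testing shortens exposure without preventing conception.

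**What to change.** For women of childbearing potential, add a serum or urine beta-hCG as follows:

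- **Table 10:** Cycle 2 Day 1, and Cycle 2 Day 28 before restaging imaging and surgery.
- **Tables 11 and 12:** Week 12 and each 4-weekly visit through Week 52 or EOT. In Table 12, the Week 12 result should be available before the first spartalizumab infusion.

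Add a sentence that study drugs are held on a positive test and stopped on confirmed pregnancy, with reporting under the existing 24-hour rule.

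The cost is a schedule amendment and up to 13 inexpensive tests per woman who completes treatment. Blood is already drawn for CBC and chemistry at every one of these visits, so no visit or draw is added. The drawback is an occasional false positive that briefly delays a dose. No test is proposed after EOT, because the tables show no later visit.

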**Table 12 Adjuvant Time and Event Table for Pathologic Non-Responders (spartalizumab, dabrafenib and trametinib)**

	Post Operat iv eh	Week 12 i	Week 16 i	Week 20 i	Week 24 i	Week 28 i	Week 32 i	Week 36 i	Week 40 i	Week 44 i	Week 48 i	Week 52 i	EOT j
Concurrent medications	X	X	X	X	X	X	X	X	X	X	X	X	X
AEs	X	X	X	X	X	X	X	X	X	X	X	X	X
PE/Vitals/ECO Ga		X	X	X	X	X	X	X	X	X	X	X	X
CBC with diff		X	X	X	X	X	X	X	X	X	X	X	X
Serum chemistry b		X	X	X	X	X	X	X	X	X	X	X	X
TSH, fT4				X			X			X			
Echocardiogram c		X			X			X			X		
12-lead EKG		X			X			X			X		X
Research Biopsy d													
If evidence of disease recurrence or metastasis													
Research Blood e		X			X			X			X		X
Research microbiome collection f		X						X					X

Disease Assessment g				X			X			X			X
Spartalizumab		X	X	X	X	X	X	X	X	X	X		
Dabrafenib and trametinib dosing	X	Continuous Daily Dosing											

- a. Includes systolic and diastolic blood pressure, pulse rate, temperature and weight.
- b. Albumin, alkaline phosphatase, total bilirubin, bicarbonate, BUN, calcium, chloride, creatinine, glucose, LDH, magnesium, phosphorus, potassium, total protein, AST, ALT, sodium.
- c. Repeat echocardiogram will be performed at month 3 and 6 and at the discretion of the investigator if there are symptoms concerning for heart failure.
- d. Should a biopsy be performed as part of standard practice, this study may request up to 4 additional cores for correlative studies.
- e. 50ml of blood will be obtained at each time point for correlative correlates.
- f. Microbiome will be collected at week 12, 36 and at recurrence. OMNIgene kits, or equivalent, will be provided
- g. PET/CT or CT of the chest, abdomen, pelvis (neck if clinically indicated) and brain MRI (or CT of the head with contrast if MRI is contraindicated).
- h. Dabrafenib and trametinib combination therapy will resume approximately two days after the patient is able to resume normal oral intake and ideally should be within 2 weeks of date of surgery. This visit could be a telephone assessment by research nurse
- i. These time points are +/- 7 days.
- j. End of treatment is defined as completion of 44 weeks of adjuvant dabrafenib/trametinib, experiencing SAE or intolerable AE mandating discontinuation of treatment or the development of progressive disease

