### 3.0 STUDY DESIGN

[figure not shown]
This is an open-label single arm Phase II study that aims to examine the strategy of altering adjuvant therapy depending on pathologic response to neoadjuvant dabrafenib and trametinib therapy. Clinical stage III B/C/D BRAF V600E/K mutation with resectable disease will be enrolled. Patients will undergo 8 weeks of neoadjuvant dabrafenib and trametinib, followed by restaging scans and then definitive surgery if disease remains resectable. Surgical pathology will be analyzed for pathologic complete response (pCR), which is defined as absence of any residual tumor by H&E assessment.

Near pCR will be defined as less than 10% viable melanoma in the surgical specimen. Pathologic partial response (pPR) is defined as less than 50% viable tumor in the surgical specimen. No pathologic response (pNR) is defined as  $\geq 50\%$  viable tumor in the surgical specimen.

Patients who achieve a pCR will continue with adjuvant dabrafenib and trametinib for an additional 44 weeks in order to complete a total 1 year of therapy. Patients who do not achieve a pCR after 8 weeks of neoadjuvant dabrafenib and trametinib will receive dabrafenib, trametinib and spartalizumab in the adjuvant setting for a total of 44 weeks. Patients with no resectable disease after neoadjuvant therapy will be removed from the study and replaced.

Longitudinal blood and tumor will be collected in accordance with the study schedule.

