### 3.3.6 Decreased Left Ventricular Ejection Fraction (LVEF)

Decreases of the left-ventricular-ejection-fraction (LVEF) have been observed in subjects receiving trametinib monotherapy and with trametinib in combination with dabrafenib.

Therefore, a baseline echocardiogram will be performed to assess for adequate LVEF function. Repeat echocardiograms will be performed every 3 months during the duration of dabrafenib and trametinib therapy or at any point if patients develop heart failure symptoms. Management will be per the guidelines in Table 8.

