### 4.4.2 ECG

12-lead ECG will be obtained as indicated in the Times and Events Tables in Section 7.2. Each 12-lead ECG will be performed after the subject has rested at least five minutes in a semi- recumbent or supine position.

$$QTc \text{ (Bazett)} = \frac{QT}{\sqrt{RR}}$$

Those QTc values greater than 480msec as calculated by the machine must be confirmed manually using Bazett's formula given below:

If there are any clinically significant abnormalities including but not limited to a QTcB > 500msec, confirm with two additional ECGs taken at least 5 minutes apart.

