#### **4.4.3 Echocardiogram**

An echocardiogram will be performed to assess cardiac ejection fraction and cardiac valve abnormalities as indicated in the Times and Events Tables in Section 7.2.

Echocardiography should include an evaluation for left ventricular ejection fraction and both right- and left sided valvular lesions. For each subject, the same procedure should be performed at the screening and as clinically warranted during the course of the study.

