## 4.8 IMAGING ASSESSMENTS

Disease assessment will include imaging (computed tomography, magnetic resonance imaging) and physical examination (as indicated for palpable/superficial lesions). At screening, an MRI or CT of the head is required. At minimum, CT of the chest, abdomen and pelvis are required but additional imaging of affected areas (neck or extremities) may be required for documentation of target lesions.

Disease assessment will be completed within 35 days prior to the first dose of study drug, then as indicated in the Time and Events Tables Section 4.3. It is not necessary to repeat radiologic assessments at the final study visit if the subject was withdrawn due to disease progression. More frequent disease assessments may be performed at the discretion of the investigator. To ensure comparability between baseline and subsequent assessments, the same method of assessment and the same technique will be used when assessing response.

Disease response will be recorded as complete response (CR), partial response (PR), stable disease (SD), or progressive disease (PD) according to RECIST 1.1 criteria .

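### Footnote c of Tables 11 and 12 fixes repeat echocardiograms at months 3 and 6, but the row it annotates marks weeks 12, 24, 36 and 48, and Section 3.3.6 requires one every 3 months throughout therapy

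*Combined protocol and SAP*

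**What the plan says.** Three places in the combined protocol and SAP set the timing of echocardiograms after baseline.

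- **Section 3.3.6 (Decreased LVEF)**: "Repeat echocardiograms will be performed every 3 months during the duration of dabrafenib and trametinib therapy", and additionally whenever heart failure symptoms appear.
- **Tables 11 and 12, echocardiogram row**: crosses at weeks 12, 24, 36 and 48 in both the pCR and the non-pCR table.
- **Tables 11 and 12, footnote c**, attached to that row with identical wording in both tables: "Repeat echocardiogram will be performed at month 3 and 6 and at the discretion of the investigator", the discretion applying where symptoms suggest heart failure.

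Section 4.4.3 (Echocardiogram) gives no interval of its own. It sends the reader to the time-and-event tables and also allows echocardiography when clinically indicated.

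On duration, Section 3.0 has patients with a pCR continue dabrafenib and trametinib "for an additional 44 weeks in order to complete a total 1 year of therapy", after 8 neoadjuvant weeks. Patients without a pCR receive the same two drugs with spartalizumab for 44 weeks.

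**The concern.** The footnote names two fixed times and makes any further repeat depend on symptoms. The row it annotates carries four fixed times, and Section 3.3.6 sets a fixed interval with no end before therapy stops. These cannot all be the schedule, and the protocol has no precedence rule between a grid and its footnote. Section 4.4.3 does not settle the matter, because it defers to the tables in which the conflict sits.

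Section 3.3.6 names LVEF decrease as a known effect of trametinib, alone and with dabrafenib, and Section 3.3.2 lists LVEF reduction among the events that call for modifying trametinib alone. This row is the working schedule for finding such a decrease. Staff who took the footnote as the rule would lose two scheduled checks while dosing continued daily. What would be lost is routine surveillance of patients without symptoms. It would also be unclear whether an echocardiogram not done at week 36 or 48 is a protocol deviation.

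**Working it through.** No sample-size or power figure is involved. The check is a comparison of texts plus simple calendar arithmetic.

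**1. Time origin of the table weeks.** Neoadjuvant 8 weeks + adjuvant 44 weeks = 52 weeks. The adjuvant tables run from a post-operative visit and week 12 to week 52, so table weeks count from the start of treatment. The surgical pause is ignored here.

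**2. Reading the grid.** The columns are post-operative, then weeks 12, 16, 20, 24, 28, 32, 36, 40, 44, 48, 52, then end of treatment. In both tables the echocardiogram crosses fall under weeks 12, 24, 36 and 48: four checks, 12 weeks apart.

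**3. Section 3.3.6 on the same scale.** One month = 52/12 = 4.33 weeks, so 3 months = 13 weeks. Every 3 months over 52 weeks gives about weeks 13, 26, 39 and 52. That is also four checks, in line with the grid's 12-week spacing.

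**4. Footnote c on the same scale.** The footnote does not say where its months start, so both origins are shown.

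| Reading | Scheduled checks | Timing (weeks) | Last check to week 52 | Share of 44 adjuvant weeks |
|---|---|---|---|---|
| Grid | 4 | 12, 24, 36, 48 | 52 − 48 = 4 weeks | 4/44 = 9% |
| Footnote, months from treatment start | 2 | 12 to 13 and 24 to 26 | 52 − 26 = 26 to 52 − 24 = 28 weeks | 26/44 = 59% to 28/44 = 64% |
| Footnote, months from surgery at about week 8 | 2 | 8 + 12 = 20 to 8 + 13 = 21, and 8 + 24 = 32 to 8 + 26 = 34 | 52 − 34 = 18 to 52 − 32 = 20 weeks | 18/44 = 41% to 20/44 = 45% |

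Counted from treatment start, the footnote matches the first two crosses and drops weeks 36 and 48. Counted from surgery, it matches none of the four. Either origin gives two scheduled checks, not four.

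**5. Could the footnote be mere commentary?** Footnotes do carry timing in these tables. Footnote f sets microbiome collection at week 12, week 36 and recurrence, and its row has crosses at weeks 12 and 36. A reader used to that convention would expect footnote c to define its row too.

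**6. Could this be a fault of text extraction?** The footnote is a complete sentence, identical in two separate tables, and the crosses agree between the tables. That makes an extraction fault implausible.

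**The case against.** The strongest reply is that the documents largely answer the question themselves. Section 3.3.6 is mandatory and unqualified, and both grids print four crosses that match it. One repeated footnote sentence stands against them. The footnote does not contain the word only and does not cancel the crosses at weeks 36 and 48. For a check to be lost, staff would have to let the footnote override both a printed cross and a body section. The clinical consequence is also small on any reading: symptom-driven echocardiograms remain throughout, and Section 4.4.3 keeps the door open for others.

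Most of this stands, and it is why the point ranks as minor. The intended schedule is recoverable, and staff working from the crosses will do all four checks. It is also fair that the gap of 26 to 28 weeks depends on counting months from treatment start. From surgery the gap is 18 to 20 weeks.

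It does not remove the conflict. By naming two times and making the rest symptom-driven, the footnote is naturally read as the full list, and no origin for its months yields four checks. That a reader can work out the right answer from elsewhere is a reason to correct the footnote rather than leave it.

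**Conclusion.** The point holds, as a minor internal inconsistency in a safety-monitoring rule. The design of a check every 3 months is not in dispute; footnote c is the outlier.

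The firm part of the size is the count: two scheduled post-baseline checks under the footnote against four under the grid and Section 3.3.6. The length of the unmonitored stretch rests on assumptions: that staff follow the footnote, that its months run from treatment start, that therapy continues to week 52, and that no symptom prompts an earlier test. On that least favourable reading, 59% to 64% of the adjuvant period follows the last routine check, instead of 9%.

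The documents give no frequency for LVEF decline, so the number of cases that the two late checks would find cannot be estimated. The primary endpoint, sample size and analyses do not depend on it.

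**What to change.** Reword footnote c in Tables 11 and 12 along these lines: *Echocardiogram every 3 months (weeks 12, 24, 36 and 48) while on dabrafenib and trametinib, and at any time if symptoms suggest heart failure.* This brings the footnote into line with its own row and with Section 3.3.6, and it removes the doubt about where the months start.

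The cost is one sentence changed in two tables. It adds no visit or test beyond those already marked.

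A separate clerical correction, which has no bearing on the frequency, can go in the same amendment. Sections 4.4.2 and 4.4.3 point to the tables as being in Section 7.2. They are in Section 4.3, as Section 4.8 correctly states.
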